Evaluation of ophthalmic lenses for myopia management

Project code: IOT-MIO-2018-01

April 26, 2021

1. State of the art

Myopia currently affects approximately 30% of the global population, although it is estimated that the prevalence will increase to 50% by 2050. According to these predictions, about 5 billion people will be nearsighted by 2050.

Although it is not clear what different factors may contribute to the onset and development of myopia, some studies have suggested that myopia is a multifactorial consequence involving numerous genetic, ethical, and environmental factors.

Experimental studies using animal models have suggested different strategies to control the growth of the eye and consequently the evolution of myopia progression. The results of these studies have shown that the visual signal related to retinal defocus controls the refractive development of the eye. Thus, visual signals in the periphery of the retina cause changes in growth that affect axial length and central refraction. On the other hand, animal studies have shown that imposing myopic defocus in the periphery inhibits eye growth.

Although the results of studies provide sufficient evidence of the efficacy of different clinical interventions for myopia control, there are still unresolved questions related to the underlying mechanisms. This includes, but is not limited to, the contribution of central and peripheral retinal regions to the regulation of eye growth, as well as the influence of aberration changes such as positive spherical aberration.

1.1. Human studies with glasses for myopia control

There are different options being worked on to prevent or delay the onset of myopia, from an optical, pharmacological, environmental, and surgical perspective. However, the option of using glasses to delay myopia progression has quite a few advantages compared to other myopia control strategies: they are easy to fit, they are well accepted and tolerated, they are affordable for most, and they are minimally invasive.

The different myopia management spectacles options that have been worked on are as follows:

- **Under-correction** for distance vision around +0.50D to +0.75D has been a strategy used in clinical practice for many years to reduce myopia progression. However, recent studies have shown that it provides no proven benefit compared to full correction.

- **Bifocal lenses** to reduce accommodative demand and/or reduce accommodative lag during near tasks. Most published studies suggest that there is no difference in myopia progression between single-vision and bifocal wearers.

[figure not shown]

Figure 1. Results of clinical studies that have evaluated the efficacy of bifocal lenses as a treatment for myopia management.

- **Progressive lenses** have been the most studied spectacle treatment. The results have shown positive effects of their use as a treatment for myopia, but these effects are questionable from a clinical point of view.

[figure not shown]

Figure 2. Results of clinical studies that have evaluated the efficacy of progressive lenses as a treatment for myopia management.

- Single vision lenses that induce positive defocus in the periphery:** These lenses are characterized by having an optical zone free of defocus and a peripheral zone that has a positive defocus induced from +1.00 to +3.50D. The results of these lenses show moderate benefits, being the lenses with smaller optical zone and higher peripheral defocus power the ones that have shown a greater delay in myopia progression.

[figure not shown]
[figure not shown]

Figure 3. Results of clinical studies that have evaluated the efficacy of single vision lenses that induce positive defocus in the periphery as a treatment for myopia management.

Previous studies in animal models have shown that retinal defocus plays an important role in the emmetropization process of the eye and therefore in the development and progression of myopia. According to published studies, optical compensation that includes an alteration of image quality in the periphery of the retina produces a decrease in myopia progression, with lenses with smaller optical zone and greater peripheral defocus showing greater efficacy. Based on previous literature, different ophthalmic lens prototypes have been developed consisting of a central optical zone surrounded by a peripheral zone that induces a reduction in optical quality.

In this study we propose to conduct a controlled study to evaluate the safety and effectiveness of the proposed ophthalmic lens prototypes as a myopia control system.

3. Hypothesis

The proposed ophthalmic lenses provide an adequate level of visual function while helping to slow the progression of myopia in myopic children.

The main purpose of this study is to evaluate the short-term efficacy in decreasing myopia progression of 2 different prototypes of proposed ophthalmic lenses, compared to a control group, in a group of myopic children.

5. Methodology

5.1. Type of study

Double-blind experimental study to analyze the effect of 2 ophthalmic lens prototypes on myopia progression. The follow-up period to evaluate the efficacy of the lens will be 6 months including a total of 4 visits.

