5.4. Procedure

- Visit 1 (Recruitment and Baseline measurements): The optometrist will provide information about the study to the parents of the children, who then signed a written consent form after any doubts will be cleared up. The optometrist also will check that the children met the inclusion criteria. In this same visit, baseline measurements will be taken. All children shall be submitted an ophthalmology exam to evaluate their ocular health, and their cycloplegic autorefraction, binocular vision, and axial length will be recorded in the case report form. Additionally, parents will complete a sociodemographic questionnaire, and the children will select the frames for their spectacles.

Once the visit is completed, the IOT team will order 2 pairs of glasses with the same prescription and customization parameters, which will be the final glasses that the participants will wear during the study period. Before delivering the glasses to the participants, a full quality control will be performed on the quality and fit of the lenses.

- Visit 2 (Delivery of glasses): Previous glasses are removed, and 2 new glasses will be delivered to be used during the study period. Verification of fit and delivery of glasses usability questionnaire.
- Visit 3 (6 months follow-up): Collection of spectacle usability questionnaire and data collection after treatment period. Ophthalmological data will be recorded after treatment including cycloplegic refraction, biometry, and usability questionnaires.
- Visit 4 (12 months follow-up): Collection of spectacle usability questionnaire and data collection after treatment period. Ophthalmological data will be recorded after treatment including cycloplegic refraction, biometry, and usability questionnaires.

Task	Responsible Partner
Recruitment	Amires
Visit 1: Patient information, verification of criteria, ophthalmological evaluation, and selection of frames.	Clinica Novovisión/Universidad Europea de Madrid/IOT
Visit 2: Delivery of glasses	IOT
Visit 3: 6 months follow-up	Clinica Novovisión/Universidad Europea de Madrid
Visit 4: 12 months follow-up	Clinica Novovisión/Universidad Europea de Madrid
Statistical analysis and final report	IOT/ Clinica Novovisión/Universidad Europea de Madrid

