5.5. Data collection and statistical analysis plan

All variables for each individual and in each phase will be collected in the data collection notebook designed for this purpose. All data will be included in a database developed for this purpose for subsequent statistical analysis. The main variables of the study will be the values of axial length and refraction with cycloplegia.

A comparative statistical analysis of absolute (mm) and relative (%) axial length growth between the lens for the management of myopia and the standard single vision lens groups will be done using the software STATA®. Absolute axial length growth will be calculated as median relative difference after 6 and 12 months of treatment as $(AL \text{ at } 6m - \text{baseline } AL) / \text{baseline } AL * 100$ and $(AL \text{ at } 12m - \text{baseline } AL) / \text{baseline } AL * 100$, respectively. Significance level will be set as p-value < 0.05 . Efficacy of myopia management lenses will be evaluated by comparing the means of relative axial length growth in children treated with myopia management lenses to that of children treated with the standard single vision group.

iot

[name]
[name]
([contact]

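### Efficacy follow-up is 6 months in 5.1 but 12 months in 5.4 and 5.5, and the efficacy comparison names no time point, so p < 0.05 could be met at either visit

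*Combined protocol and SAP*

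**What the plan says.** Section 5.1 of the combined protocol and SAP says: "The follow-up period to evaluate the efficacy of the lens will be 6 months including a total of 4 visits". The statement of purpose that follows section 3 gives no month: "The main purpose of this study is to evaluate the short-term efficacy in decreasing myopia progression".

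Section 5.4 and its task table list baseline (Visit 1), delivery of glasses (Visit 2), 6 months (Visit 3) and a further assessment: "Visit 4 (12 months follow-up): Collection of spectacle usability questionnaire and data collection after treatment period". Visits 3 and 4 both record cycloplegic refraction and biometry.

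Section 5.5 has four relevant statements:

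- Main variables: "The main variables of the study will be the values of axial length and refraction with cycloplegia".
- Growth: "Absolute axial length growth will be calculated as median relative difference after 6 and 12 months of treatment". The two formulas that follow are both percentages of baseline.
- Threshold: "Significance level will be set as p-value < 0.05".
- Efficacy: "Efficacy of myopia management lenses will be evaluated by comparing the means of relative axial length growth", lens against single vision, with no visit named.

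**The concern.** The sentence in 5.1 cannot be true as written, because the stated number of visits is reached only at 12 months. Section 5.5 does not settle the matter. It fixes the variable, scale and summary for efficacy but treats the two visits alike. Two analysts could each follow the plan and report different primary results.

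Two things are at stake. First, the 0.05 level does not bound the error of the trial's conclusion if a result at either visit is allowed to count. Second, a trial that succeeds at one visit and fails at the other has no pre-set interpretation.

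The same paragraph of 5.5 has further defects that widen the choice. It attaches the labels absolute and median to a percentage formula, although efficacy compares means. It promises growth in both mm and % without giving a formula in mm. It names refraction as a main variable but states no comparison for it.

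**Working it through.** **Visit count.** Visits within 6 months in 5.4: Visits 1, 2 and 3, so 3. Visits in 5.1: 4. The two agree only if follow-up runs to 12 months.

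**Inputs.** From 5.5: a 0.05 level and two time points. Not in the documents, so assumed: two-sided tests (critical value 1.96), a correlation r between the 6- and 12-month test statistics of 0.5 to 0.9, and 80% power at 12 months. The sample of 92 in 5.2 has no stated derivation, so the plan has no power figure to reproduce.

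**No true effect.** With Z6 and Z12 bivariate normal, mean 0 and correlation r:

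- Either direction: 1 − P(|Z6| ≤ 1.96 and |Z12| ≤ 1.96)
- In the lens's favour: 1 − P(Z6 ≤ 1.96 and Z12 ≤ 1.96)

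For independent tests the first is 1 − 0.95² = 9.75%. Numerical integration gives the rest:

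| r | Either direction (one test: 5%) | Lens's favour (one test: 2.5%) |
|---|---|---|
| 0 | 9.75% | 4.94% |
| 0.5 | 1 − 0.9093 = 9.07% | 1 − 0.9546 = 4.54% |
| 0.7 | 1 − 0.9165 = 8.35% | 1 − 0.9583 = 4.17% |
| 0.8 | 1 − 0.9219 = 7.81% | 1 − 0.9610 = 3.90% |
| 0.9 | 1 − 0.9296 = 7.04% | 1 − 0.9648 = 3.52% |

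**Lens works.** Mean of Z12 = 1.96 + 0.84 = 2.80 (80% power). The mean of Z6 is either the same or 2.80/√2 = 1.98 (ratio 0.71). The ratio 0.71 and r = 0.71 would arise if the two half-years contributed equal, independent growth.

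P(exactly one significant in the lens's favour) = P(6-month only) + P(12-month only):

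| r | Equal standardised effects | 6-month effect 0.71 times the 12-month effect |
|---|---|---|
| 0.5 | 11.3 + 11.3 = 22.6% | 4.5 + 33.7 = 38.2% |
| 0.71 | 8.6 + 8.6 = 17.2% | 2.1 + 31.3 = 33.4% |
| 0.9 | 5.0 + 5.0 = 10.0% | 0.2 + 29.4 = 29.6% |

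**Worst case only.** Suppose refraction tests, which 5.5 does not specify, were also counted at both visits. Take correlation r between visits and between variables, and r² across both. The chance of at least one p < 0.05 among four is then 16.1% (r = 0.5), 13.7% (0.7), 12.0% (0.8) or 9.8% (0.9).

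**After the fix.** One primary test, or a fixed order in which the second test is made only after the first succeeds, has a type I error of 5%.

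**The case against.** The strongest reply is that the documents lean towards 6 months. Section 5.1 ties efficacy to that period and the stated purpose is short-term, so 12 months could be read as an extension. That reading is reasonable but not secured: the purpose names no month, the visit count in 5.1 requires 12 months, and 5.5 gives both visits equal standing.

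It is also fair that 5.5 contains no rule allowing a win at either visit. The inflation is therefore conditional on that reading, and in the lens's favour it is 1.0 to 2.0 percentage points.

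The split results are also lopsided. If the 6-month effect is smaller, nearly all of them are successes at 12 months only; success at 6 months only is then 0.2% to 4.5%. That pattern reaches 5% to 11% only if the standardised effects are equal. This limits what the 10% to 38% range shows, but a 12-month-only success is exactly the result that would be disputed if 6 months were held to be primary.

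The four-test figure rests on tests the plan never specifies and carries no weight in the conclusion. Finally, this is a small study of prototypes with no declared regulatory claim. That bears on how much harm follows, but the one efficacy test still has no time point.

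**Conclusion.** The concern holds and must be fixed. Section 5.1 contradicts 5.4 and 5.5, and nothing elsewhere in the documents says which visit decides efficacy. If either visit may count, the two-sided error is 7.0% to 9.1% for assumed correlations of 0.9 to 0.5. It exceeds 5% at any correlation below 1, so only the size of the excess depends on the assumption. The split-result range of 10% to 38% depends additionally on the assumed 80% power and on the ratio of the 6- to the 12-month effect. The growth definition in 5.5 is wrong as written, whichever time point is chosen.

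**What to change.** 1. Reword 5.1 to a 12-month follow-up with 4 visits and outcome assessments at 6 and 12 months.
2. In 5.5 name one primary test: the between-group difference in mean relative (%) axial length growth from baseline to one stated time point, two-sided at 0.05. That time point is 12 months, or 6 months if the sponsor keeps the short-term aim, with 12 months then described as extended follow-up. The % scale is that of the existing efficacy sentence; if mm is preferred, amend that sentence too.
3. Correct the definitions. Absolute growth (mm) = axial length at the visit − baseline axial length. Relative growth (%) = absolute growth / baseline axial length × 100. Use the mean throughout, as the efficacy sentence already does.
4. Test axial length at the other time point next, then change in cycloplegic spherical equivalent, in that fixed order. Alternatively, label both secondary with no efficacy claim. A split of 0.025 per visit would also hold the two-visit error at or below 5% (4.65% at r = 0.5, 3.62% at r = 0.9).

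The choice should be recorded before outcomes are compared by group. The cost is wording in 5.1 and 5.5, with no added visits or measurements. The consent pages are not in the supplied text, so the sponsor should check that families were told the same duration. The downside of a fixed order is that later results cannot be claimed once an earlier test fails.

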5.2. Subjects of the study

The sample will consist of a group of 92 myopic children who must meet the inclusion/exclusion criteria indicated in Table 1 and who will be randomly assigned to one of the treatment groups:

- Control group who will receive a standard single vision lens.
- Group 1 who will wear a prototype lens based on peripheral positive defocus.

Inclusion criteria	Exclusion criteria

 - Age: 5 to 12 years - Myopia (spherical equivalent with cycloplegic) $\leq -0.50D$ - Astigmatism $< 1.50D$ - Anisometropia $< 1.50D$ - Best-corrected visual acuity $\geq 20/20$ 	
 - Patients who have received any previous treatment for myopia control, including the use of RPG contact lenses. - Participants with ocular pathology such as retinal detachment. - Participants using drugs that may affect pupillary size and accommodation or produce effects on the ocular surface. - Participants with systemic diseases that may affect their vision.

Table 1. Inclusion/Exclusion criteria

5.3. Material

5.3.1. Facilities and infrastructure

The study will be coordinated at the offices of Indizen Optical Technologies (Madrid, Spain) and the ophthalmological measurements will be performed in collaboration with Clinica Novovisión/Universidad Europea de Madrid, with a collaboration agreement to be defined. The children will be recruited by the Amires association.

5.3.2. Tests, questionnaires, and instruments for optometric and ophthalmologic evaluation:

- **Sociodemographic questionnaire:** participants' parents will complete a questionnaire that includes information regarding age, sex, ocular and general history, ocular surgeries, history of parents with myopia, age of onset of myopia, history of myopia progression and previous ocular treatments.
- **Objective refraction:** will be performed using an autorefractometer after cycloplegia using preferably 3 drops of cyclopentolate.
- **Ocular health assessment:** It will be performed according to Novovisión's standard procedures.
- **Biometry:** the axial length of the eye will be measured with the optical biometer preferably IOL Master (Carl Zeiss Meditec, Jena, Germany).
- **Binocular vision:** Distance and near phoria will be measured by Von Graefe's technique, the accommodative amplitude will be measured by Sheard method, and accommodative lag by MEM retinoscopy.
- **Usability questionnaires:** Questionnaires to assess children's satisfaction while wearing the spectacles, to record the wearing period and spectacle-associated problems and adverse effects.

5.3.3. Prototypes of ophthalmic lenses:

All lenses and frames required for the study will be provided by Indizen Optical Technologies. For the duration of the study, glasses will be provided free of charge (lenses + frames) ensuring that children always have a spare pair of glasses. In addition, we will change the lenses and glasses free of charge in case the prescription changes or the glasses break. Likewise, the ophthalmological examinations will be completely free of charge, so that the participation in the study does not entail any cost or commitment for the participants.

Children can be assigned to one of the three types of lenses to be tested:

- Control lenses: Standard spherocylindrical lenses.
- Prototype 1 lens: Lenses with a central zone that provides the patient's optimal prescription surrounded by a zone of positive defocus that increases progressively from the center to the periphery of the lens, in an asymmetrical manner between the different zones of the lens.

5.4. Procedure

- Visit 1 (Recruitment and Baseline measurements): The optometrist will provide information about the study to the parents of the children, who then signed a written consent form after any doubts will be cleared up. The optometrist also will check that the children met the inclusion criteria. In this same visit, baseline measurements will be taken. All children shall be submitted an ophthalmology exam to evaluate their ocular health, and their cycloplegic autorefraction, binocular vision, and axial length will be recorded in the case report form. Additionally, parents will complete a sociodemographic questionnaire, and the children will select the frames for their spectacles.

Once the visit is completed, the IOT team will order 2 pairs of glasses with the same prescription and customization parameters, which will be the final glasses that the participants will wear during the study period. Before delivering the glasses to the participants, a full quality control will be performed on the quality and fit of the lenses.

- Visit 2 (Delivery of glasses): Previous glasses are removed, and 2 new glasses will be delivered to be used during the study period. Verification of fit and delivery of glasses usability questionnaire.
- Visit 3 (6 months follow-up): Collection of spectacle usability questionnaire and data collection after treatment period. Ophthalmological data will be recorded after treatment including cycloplegic refraction, biometry, and usability questionnaires.
- Visit 4 (12 months follow-up): Collection of spectacle usability questionnaire and data collection after treatment period. Ophthalmological data will be recorded after treatment including cycloplegic refraction, biometry, and usability questionnaires.

Task	Responsible Partner
Recruitment	Amires
Visit 1: Patient information, verification of criteria, ophthalmological evaluation, and selection of frames.	Clinica Novovisión/Universidad Europea de Madrid/IOT
Visit 2: Delivery of glasses	IOT
Visit 3: 6 months follow-up	Clinica Novovisión/Universidad Europea de Madrid
Visit 4: 12 months follow-up	Clinica Novovisión/Universidad Europea de Madrid
Statistical analysis and final report	IOT/ Clinica Novovisión/Universidad Europea de Madrid

5.5. Data collection and statistical analysis plan

All variables for each individual and in each phase will be collected in the data collection notebook designed for this purpose. All data will be included in a database developed for this purpose for subsequent statistical analysis. The main variables of the study will be the values of axial length and refraction with cycloplegia.

A comparative statistical analysis of absolute (mm) and relative (%) axial length growth between the lens for the management of myopia and the standard single vision lens groups will be done using the software STATA®. Absolute axial length growth will be calculated as median relative difference after 6 and 12 months of treatment as $(AL \text{ at } 6m - \text{baseline } AL) / \text{baseline } AL * 100$ and $(AL \text{ at } 12m - \text{baseline } AL) / \text{baseline } AL * 100$, respectively. Significance level will be set as p-value < 0.05 . Efficacy of myopia management lenses will be evaluated by comparing the means of relative axial length growth in children treated with myopia management lenses to that of children treated with the standard single vision group.

iot

[name]
[name]
([contact]

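### Section 5.5 compares mean relative axial length growth without covariates; adjusting for age and baseline axial length would gain precision if they explain more than about 2% of growth variance

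*Combined protocol and SAP*

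**What the plan says.** Section 5.5 is the whole analysis plan. It announces "A comparative statistical analysis of absolute (mm) and relative (%) axial length growth" between the myopia management and single vision lens groups at 6 and 12 months, with significance at p < 0.05. Its statement on efficacy is "Efficacy of myopia management lenses will be evaluated by comparing the means of relative axial length growth in children treated with myopia management lenses" against the single vision group. No test, model, covariate or stratification factor is named. Baseline axial length appears only in the change score and as the denominator of the percentage.

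The relevant design facts are elsewhere:

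- Section 5.2: "The sample will consist of a group of 92 myopic children", "who will be randomly assigned to one of the treatment groups". No stratification is mentioned.
- Table 1: "Age: 5 to 12 years".
- Section 5.3.2: parents complete a "questionnaire that includes information regarding age, sex" and other history. Section 5.4 places this at Visit 1.
- Section 5.4, Visit 1: "axial length will be recorded in the case report form". Glasses are delivered at Visit 2.

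Both variables are therefore pre-treatment measurements that the trial already collects.

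**The concern.** An eight-year age band with unstratified assignment leaves room for age to account for part of the spread in eye growth. If it does, alone or with baseline axial length, a comparison that ignores both carries that spread into the standard error. The interval for the lens effect is then wider, and the power lower, than the same 92 children could give. A chance difference in mean age between arms would also move the estimate.

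Dividing growth by baseline length does not deal with this. It rescales the outcome, fits no slope on baseline length and leaves age out.

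Only precision is at stake. The unadjusted comparison is unbiased over randomisations and keeps its type I error near 5%.

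**Working it through.** **Inputs from the documents.** 92 children (section 5.2); ages 5 to 12 (Table 1); alpha 0.05 (section 5.5). The 92 comes with no effect size, SD, power or dropout allowance, so it cannot be reproduced.

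**Assumptions, none in the documents.** Two arms of 46, a two-sided test, an effect with 80% unadjusted power, and R2 (the within-arm share of growth variance explained by age plus baseline length) from 0 to 0.40. With 46 per arm, 80% power corresponds to d = 0.59 SD (0.5905 by the t test).

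**Variance.** With q covariates in a randomised two-arm trial of N children:

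variance ratio, adjusted to unadjusted = (1 − R2) × (N − 3)/(N − 3 − q)

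For N = 92 and q = 2 the factor is 89/87 = 1.023.

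**Break-even.** On variance alone, R2 = q/(N − 3) = 2/89 = 0.0225. Allowing also for the larger t critical value, for interval width:

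R2 = 1 − 1/{[(N − 3)/(N − 5)] × [t(N − 4)/t(N − 2)]²} = 0.023

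This is a multiple correlation of about 0.15.

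**Gain over the assumed range.** Power and interval width are from simulated two-covariate ANCOVA, 20,000 trials per row:

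| R2 | Variance ratio (formula) | Power | Adjusted/unadjusted CI width |
|---|---|---|---|
| 0 | 1.023 | 78.9% | 1.012 |
| 0.05 | 0.972 | 81.2% | 0.986 |
| 0.10 | 0.921 | 82.6% | 0.960 |
| 0.20 | 0.818 | 87.4% | 0.906 |
| 0.40 | 0.614 | 94.8% | 0.785 |

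In sample-size terms, R2 0.10 is worth 92/0.921 = about 100 children, and R2 0.20 is worth 92/0.818 = about 112. In 10,000 null trials, rejection was 0.048 to 0.050 unadjusted and 0.048 to 0.052 adjusted.

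**Sensitivity to N and arms.** With 83 or 74 children analysed (about 10% or 20% loss, assumed), break-even for interval width is 0.026 or 0.029. Section 5.3.3 says "Children can be assigned to one of the three types of lenses to be tested", whereas section 5.2 lists two groups. With three arms of about 31, break-even for a pairwise comparison (N = 62) is 0.035, and the interval is 2% wider at R2 0. Resetting d to 0.72 to restore 80% unadjusted power gives adjusted power within 1 point of the table.

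**The same variance seen conditionally.** The SE of the age gap between arms is SD × √(2/46). A gap of half a year shifts the estimate by (0.5/SD) × √R2 growth SDs. The unadjusted SE of the effect is √(2/46) = 0.209 growth SDs. For age R2 from 0.05 to 0.40:

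| Age SD (assumed) | SE of gap | P(gap > 0.5 y, either direction) | Shift, growth SDs | Share of effect | Share of SE |
|---|---|---|---|---|---|
| 2.31 | 0.482 | 30% | 0.048 to 0.137 | 8% to 23% | 0.23 to 0.66 |
| 1.5 | 0.313 | 11% | 0.075 to 0.211 | 13% to 36% | 0.36 to 1.01 |

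The upper ends need age alone to carry R2 0.40. The unadjusted interval already covers these shifts on average, so they are not an additional bias.

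**Can baseline length be both denominator and covariate?** Assumed: baseline mean 24 mm, SD 0.6 or 1.0; growth mean 0.15 mm, SD 0.12 mm; age R2 0.20; 46 per arm; 10,000 trials. The percentage model rejects 0.050 and 0.048 under the null, and 0.875 and 0.874 at d = 0.59. The mm model rejects 0.050 and 0.049, then 0.876 and 0.876. The double use does no harm.

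**The case against.** The strongest reply is that the benefit is unproven. R2, arm sizes, effect size and age SD are all assumed, and nothing in the documents quantifies a link between age or baseline length and growth. At R2 0.05 the gain is only about 2 power points (81.2% against 78.9% at R2 0) and a 1% narrower interval. This stands, and it is why the point is conditional and concerns efficiency only.

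Baseline length is also not shown to help. With growth in mm independent of baseline length and age R2 0.20, simulated power was 0.877 and 0.873 with age alone, and 0.873 and 0.869 with baseline length added (baseline SD 0.6 and 1.0). This stands too: age is the better-motivated covariate, and baseline length is cheap insurance at one degree of freedom.

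The three-arm power figures stay close to the two-arm ones because d was reset. At d = 0.59, 31 per arm gives about 63% unadjusted power. That is a fair caution about three arms, but it does not alter the relative gain from adjustment.

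It can also be said that section 5.5 names no test, so an adjusted comparison is not excluded. A bare comparison of means is most naturally read as unadjusted. If adjustment is intended, the covariates must be written down before the data are seen.

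Finally, section 5.5 mixes a median with means, labels the percentage formula as absolute growth, and settles neither the primary time point nor the eye analysed. These are real gaps, but an unadjusted analysis has to close them as well.

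**Conclusion.** The concern holds, as a recommended improvement and not as an error. That the plan names no covariate is certain; the size of the gain is not. With 92 children in two equal arms, adjusting for two covariates pays once they explain more than about 2% of growth variance, or about 3.5% for a pairwise comparison in three arms. The trade is lopsided: at worst about 1 power point and a 1% to 2% wider interval, against about 8 more power points than at R2 0 (87% against 79%) and a 9% narrower interval if R2 is 0.20. Because the 92 has no stated power basis, the documents show no spare power that would make this gain unimportant. Confidence is medium because R2 is unknown.

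**What to change.** Add to section 5.5 a prespecified linear model, at 6 and at 12 months, of relative (%) axial length growth on lens group, age at Visit 1 (continuous) and baseline axial length. Report the adjusted difference between lens groups with its 95% confidence interval. As supporting analyses, fit the same model to growth in mm and show the unadjusted difference. This keeps the efficacy measure already stated.

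The cost is one sentence and one regression per visit and scale in STATA, which the plan already names, with no new data or visits. The statistical price is two degrees of freedom. The number of arms in sections 5.2 and 5.3.3 should be reconciled so that the lens-group term is defined.
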